- ii) Participants will start with 1st and 2nd Line therapy as recommended by the AUA guidelines (AUA guidelines categorize treatments as 1st through 6th Lines of care) and we will record the numbers of participants that accelerate to higher lines of therapy. *Hypothesis: IC/BPS participants treated with mindfulness & yoga + Standard of care will have fewer participants who accelerate to higher Lines of care compared to those treated with Standard of care alone.*
- iii) Participants will record pain, function and other IC/BPS symptoms using validated questionnaires at baseline and at follow-up (approximately at 6 and 12 weeks of treatment). *Hypothesis: IC/BPS participants treated with mindfulness & yoga + Standard of care will have greater improvement in pain, function and other IC/BPS symptoms compared to participants treated with Standard of care alone, based on validated questionnaires.*
- iv) Cost-analysis will be performed comparing treatment groups. *Hypothesis: Cost analysis will find that those treated with mindfulness & yoga + Standard of care will incur less cost than Standard of care alone.*
- v) Qualitative outcomes will be obtained with an optional response during the weekly interviews to see how participant's feel their treatment is going. At a later time we may go back and enter quotes into qualitative software for analysis of themes. *Hypothesis: Patients in the mindfulness & yoga + Standard of care may feel more empowered about their health.*

2. Background

IC/PBS is a chronic urologic pain disorder associated with significant morbidity. It is defined by the American Urogynecological Association (AUA) as “a complex sensation (pain, pressure, or discomfort) perceived to be related to the urinary bladder, associated with lower urinary tract symptoms of more than 6 weeks duration, in the absence of infection or any other identifiable causeⁱ.” A 2015 survey of 1,982 patients with IC/BPS noted that, of the 180 treatment modalities, none were truly effective. In the survey, patients were surveyed about their usage of complementary and alternative medicine (CAM). Of those who responded, 84.2% had tried CAM and 55% had been recommended CAM by their physiciansⁱⁱ. There are many reasons as to why patients turn to CAM, including side effects experienced from traditional therapies, lack of efficacy and frustration with providersⁱⁱⁱ.

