Our primary aim is to determine whether the participants assess themselves as improving following the interventions based on the GRA at 3 months. The target population will be patients with IC/BPS who are seeking care. The current recommendation is to advise patients to undergo conservative management with self-care, behavioral modification techniques. If a patient is interested in this and fulfills study inclusion criteria then we will offer her the choice of volunteering for the study. All women will give consent prior to their enrollment, after they have had time to carefully consider whether they want to participate in the study. Research staff and clinicians will obtain consent either in clinic or via zoom. After enrollment, participants will fill out baseline surveys including:)the O'Leary-Sant Symptom and Problem Index (OSPI/OSCI)Patient Self Efficacy Questionnaire-2 (PSEQ-2), Hospital Anxiety and Depression Scale (HADS-A/D), PROMIS- Pain Interference Short Form 6B (PROMIS-PI), and a visual analog scale

In addition to the above outcomes, we will collect patient demographics, medical/surgical history and information regarding their IC/BPS (e.g. time since IC/BPS diagnosis, previous treatments for IC/BPS tried) and patient contact information. Once this information is collected, patients will also fill out an attestation of use, which they will sign/e-sign in REDCap, an affidavit that if they are randomized to mind/body they will use these daily to the best of their ability.

Randomization: Randomization assignment will be generated by computer generated randomization scheme used by appropriate personnel such as a statistician. Participants will be randomized in a 1:1 ratio by a computer generated sequence at enrollment. Randomization assignments will be completed via REDCAP. Randomization will only occur after consent has been obtained and all baseline data has been obtained.

Interventions:

Yoga & mindfulness meditation + Standard of care: Women will be asked to perform mindfulness meditation via a commercially available smartphone app and yoga through an online video tutorial (designed by a Physical Therapist expert in IC/BPS care and designed specifically for IC/BPS patients). Our online tutorial is currently in the process of being formatted however see supplemental materials for yoga flow. Patients will be instructed to perform

PROTOCOL TITLE: MYPAICE: Mindfulness and Yoga for Pain with Interstitial Cystitis Evaluation

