THERAPY ESCALATION: We will record when and what women use that is greater than 1st line and 2nd line therapies during their participation in the study. They will discuss escalation of therapy with their provider and study personnel will record the additional therapy as an outcome measure. This will be utilized to perform cost utility analysis to determine if the intervention is cost-effective.

PSEQ-2: The Patient Self-Efficacy Questionnaire Short Form is a 2 question questionnaire that has been used in multiple chronic pain conditions to

PROTOCOL TITLE: MYPAICE: Mindfulness and Yoga for Pain with Interstitial Cystitis Evaluation

document feelings of self-efficacy. The Short form is validated in chronic pelvic pain^{xiv}. This will be collected at baseline and at 12 weeks.

PROMIS-PI: The PROMIS-Pain interference short form 6B is an NIH PROMIS measure that measures the extent that pain interferes with daily activities. It is comprised of 6 questions^{xv}. This measure will be collected weekly.

HADS: This is formally called Hospital Anxiety/Depression Scale. This is a 7 item inventory that assesses generalized anxiety including: tension, worry, fear, difficulty relaxing and restlessness^{xvi}. This measure will be collected at baseline and at 12 weeks.

Euroqol-5d. (EQ-5d) This is a validated measure utilized to measure health states^{xvii}.

O'Leary-Sant Interstitial Cystitis Symptom and Problem Index:

This validated survey assesses severity of symptoms and bother in IC/BPS and is commonly used for IC/BPS trials. Symptom index, which has been explicitly analyzed in a prospective trial to detect change, and problem index are to be separately analyzed^{xviii}

Data Analysis

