Data Analysis: Between and within group differences will be evaluated using chi-square analysis as deemed appropriate by the statistician involved in study analysis (e.g. Fisher's Exact test for non-normal distributions of categorical variables and T-test for continuous variables). Differences between groups will be evaluated using Chi-square analyses for categorical variables as deemed appropriate by the statistician involved in study analysis (e.g. Fisher's Exact test for non-normal distributions). T-tests will be utilized for continuous variables, with comparison by Mann Whitney U for non-normal distributions. Within-group differences over time will be analyzed using the McNemar's test. If any baseline differences exist between the groups, a regression or multivariable analysis will determine the contribution of these differences to observed differences between groups. As the GRA and O'Leary-Sant will be collected more frequently, we plan to analyze these results with linear mixed models analysis.

Power Analysis: Power analysis was performed based on previously reported means and standard deviation from treatment effect based on GRA. We assumed that 41 patients in each arm (total 82) would be required to find a difference of 30% between group's pain scores (the primary outcome) with 80% power and alpha of 0.05. In order to achieve power we will need a total of 82 patients. Assuming an approximate 20-25% dropout or loss to follow-up rate, we will plan to randomize approximately 60-120 patients.

13. Provisions to Monitor the Data to Ensure the Safety of Subjects

A DSMB will not be monitoring safety of these procedures as the study risks are low. The intervention arm includes mindfulness and yoga, both of which have been shown to be low-risk interventions with minimal adverse events^{xix}. The control group will undergo standard of care treatments. Theoretically, there could be increased muscle soreness noted in patients in yoga treatment arm. There are no documented adverse events with mindfulness practice.

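### PSEQ-2, HADS, PROMIS-PI and VAS are not adjusted for their own baseline as a rule; always adjusting would gain precision from data already collected

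*Combined protocol and SAP*

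**What the plan says.** Section 7.1 lists the four scales as secondary endpoints. For continuous outcomes, the Data Analysis text at the end of Section 12 says "T-tests will be utilized for continuous variables, with comparison by Mann Whitney U for non-normal distributions". Linear mixed models are reserved for the GRA and O'Leary-Sant. The only mention of baseline adjustment is conditional: "If any baseline differences exist between the groups, a regression or multivariable analysis will determine the contribution of these differences" to the observed group differences.

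The baseline scores will exist. Section 12 (Study Procedures) puts PSEQ-2 and HADS in the baseline surveys together with "PROMIS- Pain Interference Short Form 6B (PROMIS-PI), and a visual analog scale", and adds: "Randomization will only occur after consent has been obtained and all baseline data has been obtained".

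On timing, Section 1.3(iii) has the questionnaires completed "using validated questionnaires at baseline and at follow-up (approximately at 6 and 12 weeks of treatment"). Under Outcome measures in Section 12, the PSEQ-2 entry reads "This will be collected at baseline and at 12 weeks", and HADS has the same two times. PROMIS-PI is weekly. VAS has no entry there. The hypothesis in Section 1.3(iii) is that the intervention arm "will have greater improvement in pain, function and other IC/BPS symptoms compared to participants treated with Standard of care alone".

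**The concern.** Three things are left open for these four scales.

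- **What is compared.** The plan does not say whether the test is on week-12 scores or on change from baseline. The hypothesis speaks of improvement, which makes change plausible.
- **When adjustment happens.** The plan has no criterion for a baseline difference. Read literally, any difference at all would trigger the regression nearly always. Read as a significance check, it would trigger rarely.
- **What adjustment means.** The covariates are unnamed. The regression could replace the t-test, or it could be an explanatory supplement, since its stated purpose is that it "a regression or multivariable analysis will determine the contribution of these differences to observed differences between groups".

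After randomisation, a baseline difference is due to chance. The gain from adjusting depends on how strongly baseline predicts outcome, not on the imbalance that happens to be observed, so imbalance is a poor trigger. At stake are wider intervals and lower power than the data allow on four secondary scales, and analysis choices still open after unmasked data have been seen. PROMIS-PI is also missing from the mixed-model sentence, although the reason given there, more frequent collection, applies to it too.

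**Working it through.** **The plan's own figure.** Section 5.3 powers the GRA response for 26% against 56%. The pooled two-sided formula at 5% and 80% power, with mean proportion 0.41, gives

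[1.96·√(2·0.41·0.59) + 0.842·√(0.26·0.74 + 0.56·0.44)]² / 0.30² = (1.363 + 0.558)² / 0.09 ≈ 41 per group.

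The stated 41 reproduces. It concerns the GRA only; no figure in the documents covers the four scales.

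**Inputs.** From the documents: 41 per arm, 1:1 allocation, alpha 0.05 (taken as two-sided). Assumed, because the documents give neither: a true effect of 0.5 SD, and a baseline-to-week-12 correlation r from 0.3 to 0.7. The check covers one follow-up time, with equal SD at both times.

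**Formulas.** Relative to a week-12 comparison (variance factor 1), change scores have factor 2(1 − r) and ANCOVA has 1 − r². Since 2(1 − r) − (1 − r²) = (1 − r)², ANCOVA is never worse than change scores, apart from the small cost of estimating the slope.

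- Power: noncentral t with standardised effect 0.5/√factor, on 80 df (79 for ANCOVA).
- 95% half-width: t × √(2/41) × √factor, with √(2/41) = 0.221. For week 12 this is 1.990 × 0.221 = 0.44 SD.
- Equivalent women per arm: 41/(1 − r²) against week-12 scores, and 41 × 2/(1 + r) against change scores.

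| r | 0.3 | 0.4 | 0.5 | 0.6 | 0.7 |
|---|---|---|---|---|---|
| Power, week-12 t-test | 61% | 61% | 61% | 61% | 61% |
| Power, change-score t-test | 47% | 53% | 61% | 71% | 82% |
| Power, ANCOVA | 65% | 68% | 73% | 80% | 88% |
| Half-width, week-12 (SD) | 0.44 | 0.44 | 0.44 | 0.44 | 0.44 |
| Half-width, change (SD) | 0.52 | 0.48 | 0.44 | 0.39 | 0.34 |
| Half-width, ANCOVA (SD) | 0.42 | 0.40 | 0.38 | 0.35 | 0.31 |
| Extra women per arm, against week-12 | 4 | 8 | 14 | 23 | 39 |
| Extra women per arm, against change | 22 | 18 | 14 | 10 | 7 |

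The formula leaves out the small cost of chance baseline imbalance. Simulated ANCOVA power (100,000 trials per cell, bivariate normal) is 64.3/67.9/72.8/79.3/87.5%, at most 0.7 points lower.

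**If the rule means test first, then adjust.** This is one possible reading, and the p-value triggers are assumed. The same simulation switches from the week-12 t-test to ANCOVA only when a baseline t-test passes the trigger.

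| r | 0.3 | 0.4 | 0.5 | 0.6 | 0.7 |
|---|---|---|---|---|---|
| Power, trigger p<0.05 | 61% | 61% | 62% | 62% | 63% |
| Power, trigger p<0.20 | 61% | 62% | 64% | 65% | 67% |
| Type I error, p<0.05 | 4.8% | 4.5% | 4.3% | 3.9% | 3.6% |
| Type I error, p<0.20 | 4.6% | 4.1% | 3.7% | 3.2% | 2.7% |

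The rule recovers 27–29% of the variance reduction at p<0.05 and 63–65% at p<0.20. Theory agrees. The share of a standard normal's variance beyond ±c is 2[c·φ(c) + tail area], which is 2(1.96 × 0.0584 + 0.025) = 0.28 for c = 1.96 and 2(1.28 × 0.1755 + 0.10) = 0.65 for c = 1.28.

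**Mann-Whitney branch.** On an assumed skewed 13-level score with a 0.5 SD latent shift (20,000 trials), Mann-Whitney has 57–58% power. ANCOVA on ranks has 61/64/68/74/82%. Both hold type I error at 4.6–5.1%.

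**The case against.** The strongest reply is that the plan is not silent. Taken literally, any baseline difference triggers a regression, and some difference nearly always exists. If that regression used the scale's own baseline and replaced the t-test, the plan would already adjust almost always, and most of the gain above would already be there. That is a fair reading, but it needs a covariate and a role that the text does not supply. Writing those in is the fix proposed here.

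Other points stand as limits:

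- The size of the gain rests on an assumed r. The option to escalate treatment at 6 weeks could change the correlation, by an unknown amount.
- The advantage over week-12 scores is not unconditional. Allowing for slope estimation, the ANCOVA factor is about (1 − r²) × 79/78. This exceeds 1 only when r² < 1/79, that is r below about 0.11, and the loss is then at most about 1% of variance.
- The figures fit PSEQ-2 and HADS best. They do not describe a mixed model for PROMIS-PI, and the VAS schedule is unclear.
- Mann-Whitney is a valid test. Preferring a baseline-adjusted rank analysis is a matter of efficiency.
- The test-then-adjust reading errs on the conservative side, so it adds no false positives.

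None of this reverses the direction of the gain or argues against the change.

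**Conclusion.** The point holds, as a free improvement and not as a validity error. No section makes a scale's own baseline a prespecified covariate for PSEQ-2, HADS, PROMIS-PI or VAS, although all four are measured before randomisation. For r between 0.3 and 0.7, unconditional adjustment beats both unadjusted forms. At an assumed 0.5 SD effect it adds about 4 to 27 percentage points of power over a week-12 t-test (65 − 61 to 88 − 61), and about 18 down to 6 points over change scores (65 − 47 to 88 − 82). Confidence is high in the direction of the gain; its size depends on a correlation the documents do not give. The GRA analysis and the sample size are untouched. O'Leary-Sant has a mixed model, but how its baseline enters is not stated. EQ-5D has no stated schedule and is left out of this point.

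**What to change.** Replace the conditional sentence with a fixed rule: every scale measured at baseline is analysed with its own baseline as a covariate, whatever imbalance is observed. Specifically:

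- **PSEQ-2, HADS, VAS:** ANCOVA at week 12, reporting the adjusted between-arm difference with its 95% interval. If VAS is collected repeatedly, use a mixed model instead, and state its schedule.
- **PROMIS-PI and the O'Leary-Sant indices:** a baseline-adjusted linear mixed model, with the week-12 between-arm difference as the estimate. Settle whether PROMIS-PI is weekly or at about 6 and 12 weeks.
- **Clearly non-normal scores:** a baseline-adjusted rank analysis, for example rank ANCOVA, as the sensitivity analysis in place of Mann-Whitney.

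Two separate, minor wording points in the same paragraph: limit McNemar's test to paired binary outcomes, and tie Fisher's exact test to small expected counts.

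The cost is analysis wording only. No new data, visits or participants are needed. The change should be made before any outcome data are compared by arm.

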- have demonstrated Hunner's ulcers on cystoscopy, treated or untreated by fulguration or steroid injection, within the last 6 months
- As our intervention requires Smartphone utilization and video usage, we will be excluding patients whose hearing or vision would interfere with ability to use the yoga video or meditation app.
- Neurogenic bladder (e.g. secondary to CVA with residual deficits, Multiple Sclerosis, Parkinsonism)
- Severe mobility impairment or physical conditions that would interfere with their ability to perform yoga as they would be unable to perform certain Yoga postures.
- Inability to speak/understand English or Spanish
- Inability to perform study follow up

4.2 Main inclusion criteria is as follows:

- Female subjects ≥18 years old

PROTOCOL TITLE: MYPAICE: Mindfulness and Yoga for Pain with Interstitial Cystitis Evaluation

- IC/BPS clinical diagnosis, which requires >6 weeks of symptoms consistent with IC/BPS and lack of other bladder pathology (such as radiation exposure, active urinary tract infection, pelvic trauma, etc.) that would explain symptoms
- English or Spanish reading/writing
- Own a Smartphone to be able to watch an online video or use Smartphone meditation app.
- Ability/willingness to participate in follow up questionnaires
- O'Leary-Sant ICSI/ICPI >6

4.3 As noted above: Adults unable to consent, pregnant women, and prisoners will not be included in this study.

4.4 As noted above: We will include English and Spanish speaking populations only. We are excluding men as we are a Urogynecology practice and therefore do not have access to that population, and the vast majority of sufferers from IC/BPS are women^{xi}. Unfortunately, we do not have the ability to recruit in other languages beyond English and Spanish, as our primary outcome measures have not been validated in other languages.

5. Number of Subjects

5.1 This is a single-center study at University of New Mexico, so the total number of subjects at the University of New Mexico is the total number of subjects for the study.

5.2 The total number of subjects to be recruited at this site is 60-120 patients.

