5.3 Sample size calculation: The primary outcome for this study is a linear mixed model of GRA variation over time. Weekly GRA and O'Leary-Sant values will be obtained on all participants. We will then further characterize patients as either treatment responder or non-responders, with treatment response defined as "moderate (+2)" or "marked (+3)" improvement on the GRA. We used previously reported outcomes from an RCT regarding impact of medication on ICBPS symptoms.

Given that we will be performing a linear mixed model, we powered our study to detect a 30% change in treatment response between groups on the GRA, with baseline response rate of 26%. We require 41 participants/group (total N=82) to obtain 80% power ($\alpha=0.05$), assuming an effect size of 0.85. Allowing for a dropout rate of 15%, we aim to randomize 94 women (47/group). We will be able to recruit the required number of participants. We see 12-15 new patients with ICBPS per month and should

be able to adequately recruit 6-7 patients/month, allowing us to meet the necessary sample of patients within 14 months of study initiation. Despite COVID-19, we still continue to care for this number of patients. The study has maximized digital & phone contact and minimized in-person contact. We foresee that we should meet our recruitment aims despite the pandemic's restrictions.

6. Study Timelines

6.1 Based on current clinic volume in the UNM division of the Urogynecology, from which we are recruiting, we estimate that recruitment of 60-120 patients will be feasible over approximately 2-3 years. Per chart review, the urogynecology division sees patients who meet criteria for this study at the rate of 10-20 per month. Assuming that approximately 25% of patients will agree to study participation (due to issues of time commitment and eligibility criteria), we believe that we will be able to recruit an appropriate number of patients in approximately 2-3 years. We believe that an additional 3 months will be needed for follow up data. We anticipate that data analysis and manuscript writing will take an additional 6-9 months.

7. Study Endpoints

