Research Experience: The Urogynecology Division at UNM has a strong history of conducting high quality research and collaboration with other investigators in the US and abroad, and has consistently met or exceeded recruitment goals on time. We have been members of the NICHD-sponsored Pelvic Floor Disorders Network (PFDN), and have met recruitment goals with high rates of follow-up and accurate data collection. In addition to PFDN research, [name] has mentored and has been the PI on multiple clinical trials and contributes multiple publications in peer-reviewed journals. Her Curriculum Vitae is attached.

Our group is well versed in the importance of adherence to protocols, timely completion of regulatory requirements, effective recruitment strategies, and the importance of the inclusion of minority subjects. Research is integral to all aspects of Divisional work; importantly, all members of the clinical team participate in research efforts. There are weekly research meetings to discuss the progress of the ongoing studies within the department, and it is an excellent forum to ensure that all involved are adequately informed of their duties, of the protocol, and of the procedures.

We do not anticipate that emergency care will be needed for this study; the urogynecology physicians are available on a 24 hour basis, 7 days per week for their patients requiring emergency care.

10. Prior Approvals

The only approval prior to commencing research will be with [name], PFPT. She is a certified yoga teacher and a pelvic floor physical therapist with extensive background in making online yoga tutorials. She is designing this yoga sequence for our study (see supplemental materials). This study was presented to [name] for approval, and the signed Departmental Review Form can be found in the “Supporting Documents” Section.

This study does not include ionizing radiation, biological specimens, or drugs.

11. Multi-Site Research

This is not a multi-site research study.

12. Study Procedures

This non-blinded randomized control trial will be conducted at the UNM Eubank clinic and SRMC Urogynecology clinic. We will recruit participants and plan to randomize approximately 60-120 participants from these sites.

Collaborating investigators will be members of the urogynecology division at UNM HSC.

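### The plan needs 82 evaluable women, but its dropout rates (15% or 20-25%) and its numbers to randomise (94 or 60-120) contradict each other, and 60-81 cannot yield 82

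*Combined protocol and SAP*

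**What the plan says.** Two places give a power calculation and agree on the evaluable number. Section 5.3: "We require 41 participants/group (total N=82) to obtain 80% power". The Power Analysis paragraph in Section 12: "In order to achieve power we will need a total of 82 patients".

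They differ on what follows:

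- **Section 5.3:** "Allowing for a dropout rate of 15%, we aim to randomize 94 women (47/group").
- **Power Analysis:** "Assuming an approximate 20-25% dropout or loss to follow-up rate, we will plan to randomize approximately 60-120 patients".
- **Section 12, opening paragraph:** "We will recruit participants and plan to randomize approximately 60-120 participants from these sites".
- **Section 5.2:** "The total number of subjects to be recruited at this site is 60-120 patients".
- **Section 6.1:** "we estimate that recruitment of 60-120 patients will be feasible over approximately 2-3 years".

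Sections 5.2 and 6.1 count women recruited. The two statements in Section 12 count women randomised. Nothing says which statement takes precedence.

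The basis of the 82 is also described in two ways. Section 5.3 says "we powered our study to detect a 30% change in treatment response between groups on the GRA, with baseline response rate of 26" per cent, and adds an effect size of 0.85 without defining it. The Power Analysis says that the calculation rests on published means and standard deviations for the GRA, then calls pain scores the primary outcome.

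**The concern.** The number to randomise is a core design figure, and here it cannot be determined. A trial that stopped at 60 would comply with 5.2, 6.1, the opening of Section 12 and the randomisation range in the Power Analysis, yet would miss the 82 that 5.3 and the Power Analysis both require. The 80% belongs to 82 evaluable women. Section 5.3's total does not leave 82 at its own dropout rate, and the Power Analysis gives a range of which only the upper part does.

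**Working it through.** **Inputs.** Control response 26%, a 30% change, 80% power and 41 per group (5.3); alpha 0.05 (5.3 and Power Analysis); 1:1 allocation (Section 12, Randomization). Assumptions not stated in the plan: the 30% is in percentage points (26% versus 56%), the test is two-sided, and it is a chi-square without continuity correction.

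**1. Reproduce the plan's figure.** With p1 = 0.26, p2 = 0.56 and mean 0.41:

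n = [1.960 × √(2 × 0.41 × 0.59) + 0.8416 × √(0.26 × 0.74 + 0.56 × 0.44)]² / 0.30²

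= [1.3633 + 0.5575]² / 0.09 = 40.99, so 41 per group and 82 in total. Power at 41 per group is 80.0%. A relative 30% change (26% versus 33.8%) would need 540 per group, so percentage points is the reading that fits.

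**2. Randomised total that leaves 82**, from 82 / (1 − d):

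- 15%: 82 / 0.85 = 96.5, so 97 (98 with equal arms)
- 20%: 82 / 0.80 = 102.5, so 103 (104 with equal arms)
- 25%: 82 / 0.75 = 109.3, so 110

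Section 5.3's 94 matches 82 × 1.15 = 94.3, which is multiplication where division is needed. The largest dropout that still leaves 82 of 94 is 1 − 82/94 = 12.8%. Within 60-120, totals up to 102 fall short at 20% dropout, and totals up to 109 at 25%.

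**3. Complete-case power.** With n = N(1 − d)/2 per group (fractions kept), power = Φ[(0.30 × √n − 1.3633) / 0.6624]. For N = 94 and d = 15%, n = 39.95, the argument is 0.804 and power is 78.9%.

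| Randomised | Dropout | Evaluable | Power |
|---|---|---|---|
| 94 (5.3's own pairing) | 15% | 79.9 | 78.9% |
| 60 (Power Analysis, floor) | 20% / 25% | 48 / 45 | 56.4% / 53.6% |
| 120 (Power Analysis, ceiling) | 20% / 25% | 96 / 90 | 86.0% / 83.6% |
| 94 (pairing not in the plan) | 20% / 25% | 75.2 / 70.5 | 76.4% / 73.6% |

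With 60 randomised and no dropout at all, power is 66.4%.

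**4. The 0.85.** Read as a standardised mean difference in a two-sided t-test, it needs 23 per group for 80% power (80.5%; 22 per group gives 78.6%). It does not lead to 41.

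**The case against.** The strongest reply is that 5.3, the section headed as the sample size calculation, names one target. That target of 94 lies inside 60-120, and at 5.3's own dropout rate it is about one point under 80%. The range also looks like an accrual estimate: Section 6.1 expects 10-20 eligible women a month with 25% agreeing, which is 2.5-5 a month, or 60-120 over 24 months. That origin is an inference, but a plausible one.

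Much of this stands. A reader might infer that the trial is planned at about 54% power, or that the whole range is inadequate. The documents support neither. The low figures arise only if randomisation stops near 60, against the plan's own requirement of 82, and the top of the range is sufficient. The conflict remains all the same, because Section 12 twice gives 60-120 as the number to randomise, and the Power Analysis attaches it to a dropout rate that does not produce it. At 2.5 women a month, even 36 months gives only 90, so a low total is a practical possibility.

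A second reply is that withdrawn women are not lost. Section 14 plans a withdrawal GRA and use of data up to withdrawal, so the real loss may differ from the complete-case figures. The plan does not say how those data enter the 3-month result, so no firm bounds on power can be drawn from it. This does not rescue 60, which is short before any loss.

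A reader might also take the mention of pain scores as a different primary outcome. The sentence before it in the Power Analysis refers to the GRA, so a wording slip is more likely.

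**Conclusion.** The point holds: the sample-size text is wrong as written. It gives two dropout rates and two numbers to randomise for one requirement of 82, and the lower part of the range (60-81) cannot meet that requirement under any dropout rate. Under one 80% label, the plan admits totals with complete-case power from about 54% (60 at 25% dropout) to 86% (120 at 20%). The error in 94 taken alone is minor.

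The power figures rest on the percentage-point reading, a two-sided test, an uncorrected chi-square and complete cases. The exact match at 41 per group supports the first three, but the sponsor must confirm them. The contradiction and the shortfall at 60-81 depend on none of these. Whether the primary analysis is the 12-week GRA or the mixed model is described differently in 5.3, 7.1 and Section 12; that is a separate matter, not settled here.

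**What to change.** State one dropout rate and one number to randomise in 5.3, the opening of Section 12 and the Power Analysis, and remove 60-120 as a randomisation target. In 5.2 and 6.1, give a recruitment number consistent with that target. It may exceed the number randomised, because randomisation follows consent and baseline data.

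**Wording only.** Keep 94 and restate power, for example: We will randomise 94 women (47 per group). With 15% [20%, 25%] dropout, about 80 [75, 70] will have a 3-month GRA, giving about 79% [76%, 74%] complete-case power for responder rates of 26% versus 56%, two-sided 0.05, chi-square without continuity correction. The sponsor should confirm that basis first. The cost is a stated power 1-6 points lower.

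**Optional, not wording only.** To keep 80%, randomise 98, 104 or 110 at 15%, 20% or 25% dropout (80.6%, 80.6% and 80.3%). That is 4, 10 or 16 more women than 94, all within the 120 already mentioned. Sixteen more take about 2-3 months at 5.3's 6-7 a month (16/7 to 16/6), or about 3-6 months at 6.1's 2.5-5 a month (16/5 to 16/2.5). Date any change of number, since Section 12 already provides for participants who have finished the study.

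In the Power Analysis, reconcile both the reference to pain scores as primary outcome and the stated basis in means and standard deviations with the GRA responder rates in 5.3. In 5.3, define the effect size of 0.85 (scale, standard deviation, source) or remove it.
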